9.1.2. Demographics

Demographic information (date of birth, sex, race) will be recorded at start of the study.

9.1.3. Medical History

Relevant medical history, including comorbidities, LVEF from echo, prior cardiac imaging and ischemic evaluation (coronary angiography, stress testing) will be captured at start of the study from the EHR.

9.1.4. Vital Signs

Most recent blood pressure, pulse will be extracted from the chart from the most recent clinic visit which is closest to enrollment.

9.1.5. Clinical Laboratory Measurements

Most recent laboratory evaluation will be extracted from the chart from the most recent lab check that closest to enrollment.

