4. STUDY DESIGN

4.1 Study Overview

This is a single ‘center’ (Gallup Service Unit- which includes two ambulatory clinics), stepped wedge cluster randomized design with 5 clusters planned. We will randomize each patient to 1 of 5 clusters, each of which has a different enrollment time point, separated 1 month apart. Each patient will receive intervention with the heart failure care delivery model at time of enrollment. Evaluations will be taken at each cross-over time point and at conclusion of 6 months. Screening data will be reviewed to determine subject eligibility. Subjects who meet all inclusion criteria and none of the exclusion criteria will be entered into the study. Prior to enrollment for each patient, a message will be sent in that patient’s chart through the EHR to the patient’s primary provider who has 7 days to opt out if they think patient should not be enrolled.

Probable Duration of Project: Total duration of subject participation will be 6 months.

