6.2 Inclusion/Exclusion Criteria

Inclusion

- Age \geq 18 years
- Seen at internal medicine or family medicine clinic at GIMC or THC in last 12 months
- Left ventricular ejection fraction \leq 40%
- Prescription at IHS pharmacy in last 12 months

Exclusion

- Primary providers opted out of inclusion for that particular patient
- Hospice care

Eligibility: Eligibility of patients will be assessed by the study team based on the patient's medical record. However, as detailed, if provider feels patient is inappropriate for enrollment, they can also opt out of enrollment. Those who meet criteria will have a EHR message sent through the chart to the primary provider. Primary providers have 1 week to opt out. If they do not opt out, patient will be automatically enrolled and placed into a randomization cluster group.

Exclusion criteria have been kept to a minimum to ensure that the study can examine the effectiveness of using this heart failure care model within a 'real world' setting.

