10. ADVERSE EXPERIENCE REPORTING AND DOCUMENTATION

10.1. Adverse Events

An adverse event (AE) is any untoward medical occurrence in a clinical investigation of a patient administered the treatment arm and that does not necessarily have a causal relationship with the treatment. An AE is therefore any unfavorable and unintended sign (including an abnormal laboratory finding), symptom or disease temporally associated with the administration of medication, whether or not related to that therapy. Adverse events will be recorded in the patient chart and a case report form (CRF.) Adverse events will be described by duration, severity, outcome, treatment and relation to GDMT if related (or unrelated). Our Data Safety Monitoring committee will perform an interim analysis of the data after 1 cluster enrollment/implemented at 30 days.

AE Severity

The National Cancer Institute's Common Terminology Criteria for Adverse Events (CTCAE) Version 3.0 should be used to assess and grade AE severity, including laboratory abnormalities judged to be clinically significant. The modified criteria can be found in the study manual. If the experience is not covered in the modified criteria, the guidelines shown in Table 1 below should be used to grade severity. It should be pointed out that the term "severe" is a measure of intensity and that a severe AE is not necessarily serious.

Table 1. AE Severity Grading

Severity (Toxicity Grade)	Description
Mild (1)	Transient or mild discomfort; no limitation in activity; no medical intervention or therapy required. The subject may be aware of the sign or symptom but tolerates it reasonably well.
Moderate (2)	Mild to moderate limitation in activity, no or minimal medical intervention/therapy required.
Severe (3)	Marked limitation in activity, medical intervention/therapy required, hospitalizations possible.
Life-threatening (4)	The subject is at risk of death due to the adverse experience as it occurred. This does not refer to an experience that hypothetically might have caused death if it were more severe.

Adverse Events Description

There are well known side effects of GDMT, which patients will be counseled on prior to initiation of therapy. Common side effects, or adverse events of therapy will be defined as in Table 2.

Table 2. AE Definitions

AE	Definition
Hypokalemia	K <3.0 mEq/L
Hyperkalemia	K >5.5 mEq/L
Hyponatremia	Na <130 mg/dL
Acute Kidney Injury	Increase in creatinine from baseline of >0.5
Hypotension	SBP <90 mmHg

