11.2. Demographic and Baseline Characteristics

The following demographic variables for each patient upon enrollment will be summarized: race, tribal affiliation, gender, age, BMI.

The following clinical variables and baseline characteristics will be summarized: most recent blood pressure and heart rate, baseline creatinine, baseline potassium, most recent brain

natriuretic peptide, if any heart failure hospitalization in last 12 months, ischemic or non-ischemic cardiomyopathy based on coexisting validated ICD for ischemic cardiomyopathy [ICD codes: ICD 9 414.8, ICD 10 I25.5]), comorbidities to include coronary artery disease, diabetes, chronic kidney disease (including stage, end-stage renal disease), atrial fibrillation, hypertension, hyperlipidemia, left ventricular ejection fraction on most recent echocardiography, and prior cardiac studies including coronary angiography, stress test, or cardiac MRI.

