11.3. Analysis of Primary and Secondary Endpoints

To assess the effectiveness of our intervention, measurement of rates of GDMT, including each specific medication of ACE inhibitors, ARB, ARNI, beta-blockers, MRA, SGLT2 inhibitors will be performed at baseline, at each cross-over time point. The main analysis of our stepped wedge design will be based on a logistic mixed-effects model which will contain a random intercept to account for between-cluster variability, a fixed effect parameter for time, and a group indicator variable for the treatment for each subject and time to capture treatment differences over time.

Safety and tolerability data will be summarized by intervention group.

Adverse event rates will be coded by body system and MedDra classification term. Adverse events will be tabulated by treatment group and will include the number of patients for whom the event occurred, the rate of occurrence, and the severity and relationship to newly started therapy.

Statistical Analysis: The primary analysis will utilize the intention to treat principle. A generalized linear model will be used to assess the relationship between randomization cluster status and the primary outcome. The model will use a log-link and independent correlation structure to allow for calculation of adjusted risk ratios. Statistical significance will be based on a P value of <0.05. For categorical secondary outcomes, a similar generalized linear modeling approach will be used. For continuous secondary outcomes, a generalized linear model will be used.

Assessment of contamination: Providers may learn to better treat heart failure as consistent with evidence-based therapies over time. Given we are not clustering by provider, but rather patients, it is possible that providers will take what is being implemented on their patient that is in an active implementation phase, and apply it to a patient in a non-active implementation phase. Therefore, there is a high risk of contamination. However, with the stepped wedge design, we will be able to also see how GDMT rates increase over the study period for those clusters who are not immediately in an active implementation arm. We will be able to better understand if increases in GDMT are related to the intervention or just due to increases over time due to improved knowledge of providers over time.

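### The acute kidney injury comparison has no fixed creatinine reference, because the only baseline laboratory rule hangs on an enrollment date that the protocol defines in two ways

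*Combined protocol and SAP*

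**What the plan says.** Table 2 in section 10.1 defines AKI as "Increase in creatinine from baseline of >0.5". It gives no unit and does not identify the draw that serves as baseline; the synopsis and section 5.3 use the same definition. The one rule for taking a pre-treatment laboratory value is in 9.1.5 (Clinical Laboratory Measurements): "Most recent laboratory evaluation will be extracted from the chart from the most recent lab check that closest to enrollment". Section 11.2 lists "baseline creatinine, baseline potassium" among the characteristics to be summarised, without linking them to the AKI rule.

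Enrollment has two meanings. In section 4.1 the clusters are groups "each of which has a different enrollment time point, separated 1 month apart", and "Each patient will receive intervention with the heart failure care delivery model at time of enrollment". In section 6.2, if the primary provider does not opt out, the "patient will be automatically enrolled and placed into a randomization cluster group", which puts enrollment before the cluster is known.

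For the analysis, section 11.3 says "Adverse events will be tabulated by treatment group". No rule divides a patient's time or events between control and intervention. Section 9.1.4 (Adverse Events) does record start and stop dates and relation to therapy. Medications are recorded again at every cross-over (9.1.1); creatinine has no matching rule. Section 11.2 also lists "chronic kidney disease (including stage, end-stage renal disease" among the comorbidities, and section 6.2 does not exclude such patients.

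**The concern.** Every patient in clusters 2-5 contributes both control and intervention time, so a change-from-baseline event needs a reference that is valid in both phases. A single value cannot provide this. If it is drawn at implementation, control-time creatinine is compared with a later value, and a lasting rise under usual care is absorbed into the baseline. If it is drawn at study start, change that builds up while the patient waits is still in the difference when treatment begins and can be counted there.

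AKI is a named safety endpoint of a model that starts and titrates drugs. Two analysts could each follow the protocol and produce different AKI tables. Either table could show a gap between phases that the drugs did not cause.

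**Working it through.** The plan states no figure for AKI, so there is none to reproduce.

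**1. Timeline.** Inputs: five clusters (4.1) and 30-day steps with cluster 1 at time 0 (4.4). The implementation day of cluster k is 30 × (k − 1), that is 0, 30, 60, 90 and 120. Cluster 1 has no control time and no gap, so the problem concerns clusters 2-5, or 4/5 = 80% of patients if clusters are equal. On the study-start reading (6.2) the mean gap from enrollment to treatment over all clusters is (0 + 30 + 60 + 90 + 120)/5 = 60 days. 9.1.5 sets no maximum age, so these gaps are lower limits on the age of the value.

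**2. Time since baseline.** Take 20 patients per cluster (11.4) and follow-up to day 180 for everyone (assumed from the 6-month duration in 4.1).

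- Control time: 20 × (0 + 1 + 2 + 3 + 4) = 200 patient-months. Intervention time: 20 × (6 + 5 + 4 + 3 + 2) = 400.
- Implementation-date reading (4.1): all 200 control patient-months precede the baseline.
- Study-start reading, control: mean time since baseline = (30² + 60² + 90² + 120²)/2 ÷ 300 = 13,500/300 = 45 days.
- Study-start reading, intervention: (5 × 180² − 27,000)/2 ÷ 600 = 67,500/600 = 112.5 days.

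**3. Size with no drug effect.** Simulation of 200,000 patients in five clusters, creatinine monthly to day 180, flagged if the value minus baseline exceeds 0.5. The documents give no creatinine behaviour, so every row is an assumption (mg/dL). Entries are % of tests flagged, control / intervention, with the intervention-to-control ratio in brackets.

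| Assumed behaviour | Baseline at study start | Baseline at implementation | One baseline per phase |
|---|---|---|---|
| Stationary noise, SD 0.2 | 3.87 / 3.85 (0.99) | 3.81 / 3.88 (1.02) | 3.87 / 3.88 (1.00) |
| Transient +0.8 steps, 2% per month | 1.94 / 1.90 (0.98) | 1.98 / 1.92 (0.97) | 1.94 / 1.92 (0.99) |
| Rise 0.02 per month | 5.19 / 7.16 (1.38) | 2.86 / 5.90 (2.06) | 5.19 / 5.90 (1.14) |
| Rise 0.05 per month | 8.21 / 16.24 (1.98) | 1.80 / 10.71 (5.95) | 8.21 / 10.71 (1.30) |
| Permanent +0.8 steps, 2% per month | 3.98 / 8.14 (2.05) | 0.02 / 5.22 (about 240) | 3.98 / 5.22 (1.31) |
| Patient-specific wandering, SD 0.10 per month, mean 0 | 2.55 / 4.62 (1.81) | 2.52 / 3.20 (1.27) | 2.55 / 3.20 (1.25) |
| Fall 0.02 per month | 2.81 / 1.98 (0.71) | 5.18 / 2.52 (0.49) | 2.81 / 2.52 (0.90) |
| Fall 0.05 per month | 1.78 / 0.76 (0.42) | 8.14 / 1.45 (0.18) | 1.78 / 1.45 (0.82) |

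Noise SD is 0.2 in the rise and fall rows, 0.15 with wandering and 0.1 with steps. The ratio of about 240 arises because the control rate is almost zero: each permanent rise in control time has become the baseline.

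**4. Patients flagged early in treatment.** With wandering SD 0.15 per month and noise SD 0.15, 6.7% of patients are flagged in their first 30 treated days with a study-start baseline, against 2.7% with a baseline reset at implementation. In 100 patients that is about 7 against 3. Counting only patients not already flagged in control time lowers 6.7% to 3.8%.

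**The case against.** There are four serious objections.

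- **Direction.** A reader might infer that both readings must make the intervention look more nephrotoxic. The documents do not support that, since they give no course of creatinine over time. Transient changes or stationary noise produce no bias. With a baseline at implementation and a fall of 0.03 per month (wandering and noise SD 0.15), control flags exceed intervention flags: 6.1% against 3.6% of tests, or 7.2% against 3.6% if the day-0 test counts as control. The study-start reading also reverses under a pure fall. It need not reverse if patients also wander: with a fall of 0.02 per month and wandering SD 0.10-0.15 its ratio is still 1.41-1.65. This objection stands, and the direction has to be stated conditionally.
- **Onset dates.** Section 9.1.4 records start dates and relation to therapy, which could keep an AKI that began in usual care out of the intervention count. This stands in part: it removes most of the 6.7% versus 2.7% contrast. But a date of onset itself depends on which baseline is used, and no rule tells the analyst to apply it.
- **Inferred link.** Table 2 does not cite 9.1.5, which sits among the baseline descriptors. The supplement, the study manual and the detailed SAP promised in section 11 are not in these documents and may say more. It is therefore an inference that the 9.1.5 value is the AKI baseline. If it is not, the documents name no baseline at all.
- **End-stage renal disease.** Section 11.2 lists it only as a comorbidity to summarise. No prevalence is given, and false flags could fall in both phases. The documents do not support a claim that these patients bias the result against the intervention. What stands is that a fixed 0.5 rule makes no allowance for them.

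**Conclusion.** The concern holds in conditional form. Enrollment has two meanings, only one baseline laboratory value is specified, and neither reading gives a reference that suits both phases in clusters 2-5. The AKI comparison can therefore be biased with no drug effect. The bias runs against the intervention if creatinine rises, if rises persist, or if patients wander from their starting value. It is little or none if changes are transient, and can run the other way if creatinine falls. Over mean changes of ±0.02 per month the null ratio runs from 0.71 to 1.38 with a study-start baseline and from 0.49 to 2.06 with an implementation baseline. These sizes rest wholly on assumed creatinine behaviour, monthly testing in both phases and follow-up to day 180; only the timeline arithmetic comes from the documents.

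This bears on a secondary safety endpoint and leaves the primary endpoint untouched. It should be settled before the safety tables are produced.

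**What to change.** Define in 9.1.5, Table 2 and the SAP:

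- **Reference value.** For control time, the last creatinine before study day 0; for intervention time, the last creatinine before that patient's implementation date (the same value in cluster 1). Use one meaning of enrollment in 4.1, 6.2 and 9.1.5.
- **Phase assignment.** Assign each AKI by its recorded onset date, and do not count as an intervention event one that began in control time.
- **Exposure.** Report AKI per person-time or by time since the reference value. Phase-specific baselines alone leave a difference because intervention follow-up is longer: 4.7% against 6.2% of tests with no drug effect, at wandering and noise SD 0.15.
- **Detection.** State beside the table that study-ordered chemistry follows only after therapy is initiated (9.1.5, Blood Chemistry Profile), which favours finding AKI in intervention time. The new reference values do not cure this.
- **End-stage renal disease and unit.** Report patients with end-stage disease at baseline separately from the main AKI count, and state the creatinine unit.

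The cost is SAP and case report form wording, slightly more analysis work and a slightly smaller AKI denominator. Outcomes are already to be taken from medical records, and end-stage status and onset dates are already to be recorded.

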9.1.4. Adverse Events

Information regarding occurrence of adverse events will be captured throughout the study. Duration (start and stop dates), severity/grade, outcome, treatment and relation to guideline-directed medical therapy will be recorded.

9.2 Clinical Laboratory Measurements

9.1.5. Blood Chemistry Profile

After initiation of a recommended medical therapy by the study team, the team will order basic metabolic panel if clinically appropriate based on predetermined protocols (see supplement), which is the typical standard of care when starting certain medications (all but beta blockers). Blood will be obtained at the GIMC lab and will be reviewed by the study team for determination of serum sodium, potassium, chloride, bicarbonate, random glucose, BUN, creatinine.

10. ADVERSE EXPERIENCE REPORTING AND DOCUMENTATION

10.1. Adverse Events

An adverse event (AE) is any untoward medical occurrence in a clinical investigation of a patient administered the treatment arm and that does not necessarily have a causal relationship with the treatment. An AE is therefore any unfavorable and unintended sign (including an abnormal laboratory finding), symptom or disease temporally associated with the administration of medication, whether or not related to that therapy. Adverse events will be recorded in the patient chart and a case report form (CRF.) Adverse events will be described by duration, severity, outcome, treatment and relation to GDMT if related (or unrelated). Our Data Safety Monitoring committee will perform an interim analysis of the data after 1 cluster enrollment/implemented at 30 days.

AE Severity

The National Cancer Institute's Common Terminology Criteria for Adverse Events (CTCAE) Version 3.0 should be used to assess and grade AE severity, including laboratory abnormalities judged to be clinically significant. The modified criteria can be found in the study manual. If the experience is not covered in the modified criteria, the guidelines shown in Table 1 below should be used to grade severity. It should be pointed out that the term "severe" is a measure of intensity and that a severe AE is not necessarily serious.

Table 1. AE Severity Grading

Severity (Toxicity Grade)	Description
Mild (1)	Transient or mild discomfort; no limitation in activity; no medical intervention or therapy required. The subject may be aware of the sign or symptom but tolerates it reasonably well.
Moderate (2)	Mild to moderate limitation in activity, no or minimal medical intervention/therapy required.
Severe (3)	Marked limitation in activity, medical intervention/therapy required, hospitalizations possible.
Life-threatening (4)	The subject is at risk of death due to the adverse experience as it occurred. This does not refer to an experience that hypothetically might have caused death if it were more severe.

Adverse Events Description

There are well known side effects of GDMT, which patients will be counseled on prior to initiation of therapy. Common side effects, or adverse events of therapy will be defined as in Table 2.

Table 2. AE Definitions

AE	Definition
Hypokalemia	K <3.0 mEq/L
Hyperkalemia	K >5.5 mEq/L
Hyponatremia	Na <130 mg/dL
Acute Kidney Injury	Increase in creatinine from baseline of >0.5
Hypotension	SBP <90 mmHg
Bradycardia	HR <50 bpm
Urinary Tract Infection (UTI)	Symptoms of UTI and urinalysis/urine culture consistent with infection and/or treated by primary provider for UTI

Candidal vulvovaginitis	Consistent symptoms of infection and/or treated for presumed infection
-------------------------	--

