7. INTERVENTIONS

7.2 Intervention: Heart Failure Telemonitoring Care Delivery Model

This project was implemented as an Indian Health Service Innovations Award to improve quality of care for patients. Once patients are at their intervention time point, they receive implementation of our designed HF QI model. As part of this model, all patients are given a home BP cuff (Omron 5 arm cuff) for home BP monitoring. Protocols for each step of this model are detailed in the supplement. However, in brief, as part of the intervention, these protocols allow the study team to identify which, if any recommended guideline-directed medications are missing, identify any contraindications to therapy, and initiate therapy as directed if no contraindications are identified. Prescriptions for the therapy are made, appropriate follow-up lab testing ordered if needed, and patients are called by the study team to discuss the therapy and recommendations. Getting patients are low doses of all 4 therapy (or all therapies they are eligible on) is prioritized by the study protocol, and then doses could be secondarily uptitrated per recent HF Expert Consensus Statement.[8] There are protocols for overall model, and initiation and titration of all medications. Utilizing home blood pressure monitoring, medications were added and titrated as directed by study protocols, with patients coming in for lab work as recommended by the study protocol. All medication changes, lab work, home BP and HR readings, will be documented in the EHR and sent to the PCP. Please see supplement for flowcharts utilized in this study. Overall model is shown in Figure 2.

Figure 2. Overview of Model to Improve Heart Failure Care in Navajo Nation

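### The adverse-event definition conflicts with the planned by-group comparison, and unequal monitoring and exposure will tend to inflate adverse events in intervention time

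*Combined protocol and SAP*

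**What the plan says.** **Definition.** Section 10.1 defines an AE as an untoward occurrence "in a clinical investigation of a patient administered the treatment arm". Its next sentence describes a sign, symptom or disease "temporally associated with the administration of medication, whether or not related to that therapy". Section 10.2 defines a serious AE (SAE) as any AE with a serious outcome, so it inherits whatever restriction 10.1 carries.

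**Planned comparison.** Section 11.3 states: "Safety and tolerability data will be summarized by intervention group". It then plans AE tables by treatment group with numbers of patients, rates, severity and relationship. Section 3.2 lists differences in adverse events among the secondary objectives.

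**Measurement.** Section 7.2 says: "Once patients are at their intervention time point, they receive implementation of our designed HF QI model". As part of that model "all patients are given a home BP cuff (Omron 5 arm cuff) for home BP monitoring", and the home BP and heart-rate readings go into the electronic record. On laboratory tests, Section 9.1.5 (Blood Chemistry Profile) says: "After initiation of a recommended medical therapy by the study team, the team will order basic metabolic panel if clinically appropriate". Section 7.3 describes control time as usual treatment directed by the primary care physician and sets no measurement schedule.

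**Thresholds.** Table 2 lists eight AEs. Six are numerical: low and high potassium, low sodium, a creatinine rise, SBP below 90 mmHg and heart rate below 50 bpm. The other two are urinary tract infection and candidal vulvovaginitis.

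**The concern.** There are two separate problems.

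The first is textual. If 10.1 is followed to the letter, an event in a patient still in control time is not an AE, yet 11.3 needs such events to fill its control column. Two people extracting data under this protocol could reasonably build different tables.

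The second would remain after the wording is repaired. A potassium of 5.6 mEq/L or an SBP of 88 mmHg becomes an AE only if someone takes the sample or the reading. The intervention adds panels and home readings, and control time does not. With identical true risk, more events would be found under the intervention.

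AEs are listed secondary endpoints (Synopsis and Section 5.3). The interim review 30 days after the first cluster starts is for safety, and the interim paragraph of 11.3 allows stopping for unexpected adverse events. An apparent excess of hyperkalemia, kidney injury or hypotension could be partly an artefact of monitoring, and the planned tables give no way to tell how much.

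**Working it through.** The plan gives no figure for the safety comparison, so there is nothing to reproduce. The check sets the text side by side and then does simple arithmetic.

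**1. Whose events count**

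- Restricting text: 10.1 (treatment arm), inherited by 10.2.
- Wider text: 9.1.4 (Adverse Events) captures AEs for the duration of the study. Section 10.2.1 collects SAEs from enrolment of the first cluster, related to implementation or not, and that window includes the control time of clusters 2 to 5. Sections 3.2 and 11.3 compare AEs. The Synopsis takes outcomes from medical, hospital and billing records.

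These statements cannot all be followed as written.

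**2. What each condition adds**

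- Intervention time: usual-care measurements, plus study-ordered panels where judged appropriate, plus home BP and heart-rate readings.
- Control time: usual-care measurements only.
- AEs that depend on a measured value: 6 of 8 in Table 2.
- Safeguards: the documents set no equal ascertainment, test count, tested-patient denominator or caveat. Extraction blinded to cluster (Section 8.2) cannot find a test that was never done.

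**3. Exposure**

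Inputs: five clusters starting at months 0, 1, 2, 3 and 4 (Section 4.4), 20 patients per cluster (Section 11.4) and a six-month study (Section 1).

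- Control: 0 + 1 + 2 + 3 + 4 = 10 cluster-months; 10 × 20 = 200 patient-months. Cluster 1 contributes none.
- Intervention: 6 + 5 + 4 + 3 + 2 = 20 cluster-months; 20 × 20 = 400 patient-months.
- Ratio: 400 / 200 = 2.0.

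If observation stops at month 5, intervention time is 15 × 20 = 300 and the ratio is 1.5. If each patient is followed for six months after implementation, it is 5 × 6 × 20 = 600 and the ratio is 3.0. The ratio does not depend on cluster size as long as clusters are equal.

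**4. Detection (illustration; every testing rate, event rate and duration here is assumed)**

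Observed rate = true rate × probability of being measured. With equal true rates, the observed rate ratio is the ratio of those probabilities. Take 80% measured per month under intervention:

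| Measured per month, control | Observed rate ratio | Expected events, intervention vs control, at a true 5% per month |
|---|---|---|
| 10% | 8.0 | 16 vs 1 |
| 20% | 4.0 | 16 vs 2 |
| 40% | 2.0 | 16 vs 4 |
| 80% | 1.0 | 16 vs 8 |

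For example, 400 × 0.05 × 0.80 = 16 and 200 × 0.05 × 0.10 = 1. In the last row testing is equal, yet raw counts still differ 2:1 because of exposure.

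The chance of a nominal p < 0.05 on the rates was simulated with an exact conditional test of two Poisson counts. Down the four rows it is about 78%, 54%, 21% and 4%. At a true rate of 2% it is about 14%, 10%, 5% and 3%, while the expected rate ratios are unchanged. The AE paragraphs of 11.3 specify no such test.

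Persistence matters too. With evenly spaced tests, detection is about min(1, duration / interval). For intervals of 1 month (intervention) and 3 months (control):

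- lasting 0.5 month: (0.5/1) / (0.5/3) = 3.0
- lasting 2 months: 1 / (2/3) = 1.5
- lasting 3 months or more: 1 / 1 = 1.0

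The direction follows from the text. The size depends on testing frequency and on how long the abnormality lasts, and the documents give neither.

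**The case against.** The strongest reply has four parts.

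**The definition is loose wording.** One phrase in 10.1 stands against several sections that plainly intend control-time capture, and its second sentence refers to medication, which usual-care patients also take. This stands. A reader might infer that control-period events will not be counted at all. The documents do not support that; they support a contradiction that has to be reconciled.

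**Usual care also measures.** Section 9.1.5 calls the panel typical standard of care when certain drugs are started, and record review could find usual-care results. This stands as well. A reader might infer that laboratory tests happen only under the intervention, but only the study-ordered ones do. Control detection is lower and unscheduled, not nil. The home-cuff difference is clearer, although Table 2 does not say which readings count. The detailed testing protocols are in a supplement that is not among the documents, so the gap cannot be sized.

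**Obvious corrections can mislead the other way.** Usual-care tests may be ordered because a patient is unwell, so rates per test or per patient tested could inflate the control column and hide real harm. Discarding home readings would miss events, because titration takes place at home. Emergency and urgent visits may be prompted by study calls. These cautions limit the fix.

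**Sound outcomes already exist.** Mortality and heart-failure hospitalizations are planned, record-based outcomes, and Section 11 defers detail to an SAP still to be written. True, but neither gives the AE tables comparable ascertainment or a denominator.

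**Conclusion.** The point holds in limited form. Section 10.1, and 10.2 through it, must be reconciled with 3.2, 9.1.4 (Adverse Events), 10.2.1 and 11.3. Apart from the wording, six of the eight Table 2 events are open to unequal detection, and the by-group table will tend to show an excess under intervention for that reason alone.

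A reader might take a specific spurious ratio, such as 2 to 3, from testing every 1 to 1.5 months against every 3 months. The documents do not support it: those intervals are assumed, and the ratio falls to 1.0 for abnormalities that outlast the longer interval. The firm number is exposure, about 200 against 400 patient-months given five equal clusters of 20 and six months of observation. Raw patient counts are therefore not comparable even with equal risk and equal testing.

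Nor is the whole safety question left unanswered: deaths and hospitalizations depend much less on monitoring. The primary efficacy endpoint is unaffected. This should be corrected before the SAP is finalised.

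**What to change.** - **Section 10.1:** reword so that one AE definition applies to control and intervention time from day 0, and align 10.2 with it.
- **Section 11.3 and the SAP, denominators:** tabulate by condition (control time, intervention time), giving AE rates per patient-month rather than patient counts alone. Beside them show laboratory, BP and heart-rate measurements per patient-month in each condition.
- **Source of reading:** list events found only by home cuff separately from those found at clinic, emergency or hospital readings, and still report all of them.
- **Interpretation:** label laboratory- and vital-sign-defined comparisons as descriptive and subject to detection differences. Use per-test rates at most as a sensitivity display.
- **Lead comparison:** rest the between-condition safety comparison mainly on deaths and hospitalizations.

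None of this changes patient care or adds tests. The cost is rewording, a little more extraction from the electronic record (measurement counts and the source of each reading), and less prominent laboratory and vital-sign comparisons.
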